The overarching goal of this proposal is to a) assess the feasibility and preliminary validity of **home-based delivery of TeleNP** to patients with suspected AD, referred for cognitive assessments in a Neurology Clinic; and b) elucidate whether TeleNP is equivalent to face-to-face evaluation (FF) for diagnostic adjudication of atypical versus typical AD. To accomplish these goals, we will conduct a **pilot clinical trial** of two testing modalities, TeleNP versus FF, for delivery of neuropsychological evaluations. Neurologist-referred patients with typical (i.e., memory-predominant; n=40) and atypical (i.e., complex and/or non-memory predominant; n=40) presentations of *possible* AD will be enrolled in the study. Care partners of participants will also be consented to the study and included in stakeholder surveys/interviews. Using a cross-over design, all participants will undergo evaluations (clinical interview + Core Battery of cognitive tests) in both modalities, approximately 4-6 weeks apart to account for potential practice effects. Although all participants will be referred due to suspected AD, the neuropsychologist will be blinded to the specific diagnosis (i.e. typical versus atypical) from the neurologist. The Core Battery will include measures of memory, executive, visuospatial, and language functions. To further minimize practice effects, alternate assessment forms will be implemented and order of test forms will be counterbalanced. Some tests are not readily adaptable to video-based delivery due to tactile/physical stimuli; as such, we will assess whether a Flexible Assessment (i.e., option to include additional tests, after completion of Core Battery) in the FF modality alters diagnostic conclusions. Finally, in an exploratory aim, we will identify stakeholder perspectives of TeleNP that inform pragmatic implementation of remote neuropsychological evaluations. Our Aims are:

Aim 1: Determine the validity of home-based video administration of neuropsychological tests (TeleNP) for assessing AD. 1a: Are cognitive test results equivalent across TeleNP and FF conditions in patients with suspected AD? 1b. Is this equivalence consistent across referral diagnoses (i.e., Typical vs. Atypical AD)? *This Aim will test the validity of cognitive measures assessed with TeleNP and determine whether the validity of TeleNP differs based on referral diagnosis.*

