IV. Research Methods

A. Description of Population to be Enrolled:

Clinical Trial Participants (Patients):

We will recruit 80 patients from the **UCH Memory Disorders Clinic** (considering possible screen fails, up to 150 may ultimately be recruited). To understand the feasibility and preliminary validity of TeleNP, we will enroll 1) 40 adults with suspected **typical** AD (i.e., memory-predominant) and 2) 40 adults wherein AD is on the neurologist's diagnostic differential, but the presentation is **atypical** (i.e., complex/non-memory predominant presentations). The typical and atypical AD groups will range in severity from MCI to mild dementia (based on referring neurologist's determination); this is consistent with current conceptualizations of AD, in which clinical syndrome (AD) is distinct from severity of presentation (MCI; dementia).^{1, 2}

All participants with suspected AD will be referred by neurologists. Our specific inclusion/exclusion criteria will be:

Inclusion criteria:

Eligible participants will be adults \geq 60 years and <90 years who are undergoing evaluation for possible AD and whose severity ranges from MCI to mild dementia. Of note, we are excluding individuals aged 90 and over, as recent studies suggest that individuals in the oldest-old category differ from other individuals with MCI or dementia in terms of risk factors for AD and prevalence of non-AD pathologies.²¹⁻²³ In addition, limited age-referenced normative data for neuropsychological tests are available for individuals 90 and over, which impacts our ability to address Aims 1 and 2.

Eligible participants must carry a diagnosis of either suspected typical AD or atypical AD, based on the referring neurologist's diagnosis.

- Typical AD: Defined as a memory-predominant presentation of AD.
- Atypical/Complex AD: Defined as a complex (i.e., AD is under consideration, but other diagnoses may be included in neurologist's differential diagnosis) and/or non-memory predominant phenotype of AD.

Both patient groups will be based solely on the neurologist's clinical diagnosis after the initial Neurology visit, and in the absence of formal neuropsychological test results, to minimize circularity.

Exclusion criteria:

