Incorporation of Results into Clinical Care: Because the set battery used in the FF assessment uses validated tests that are normally used for these patients in clinical care, it is likely that patients in this study *will not* undergo a separate standard of care neuropsychological assessment. Therefore, a brief research overview of the results of the FF assessment will be provided to the referring neurologist and the participant after both conditions are complete (and posted to Epic Medical Record as a research note), for use in their clinical care. Based on a

national survey, the median time between neuropsychological assessment and completion of reports is 3 weeks; our proposed time is slightly longer than the median, but remains within an expected range for clinical reports.³¹ Of note, when considering the amount of time between referral and scheduled date of assessment in SOC (often on the order of months), our window will likely be shorter/faster than SOC given dedicate research time. If any safety, psychological or other signs of distress related to potential diagnosis of AD are noted during either assessment, appropriate referrals will be coordinated by Drs. [name] and [name]. Drs. [name] and [name] will coordinate with the neurologist to determine if prompt discussion of the first assessment is clinically prudent. The research note posted to Epic EMR will include a brief background/history, table of scores for FF condition, and summary/recommendations, consistent with standard of care approaches.

C. Outcome Measure(s):

Aim 1: Equivalence of Cognitive Test Results: *The goal of this Aim is to test the concurrent validity of cognitive measures across testing modalities and determine whether the test results differ based on referral diagnosis.* Z-scores will be calculated based on age-referenced normative data for each cognitive test (Table 1) in the Core Battery. For data reduction purposes, a mean z-score for each cognitive domain will be used (i.e., memory, executive functions, spatial abilities, language). This will allow us to address whether neuropsychological test results are equivalent across modality (i.e., FF vs. TeleNP) and whether complexity of referral impacts comparability of test results.

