F. Statistical Analysis Plan:

For **Aim 1**, we will adopt an equivalence testing framework. The null hypothesis is that there is an average difference of at least .5 SD units in the difference in the z-scores, where .5 SD defines a potentially clinically meaningful difference. The alternative hypothesis is that the mean of the

difference in the z-scores is zero. This is the reverse of standard statistical testing. We elected a .5 SD margin as an initial threshold for a clinically meaningful difference; the reason for this decision is that once an individual reaches a level deemed to be clinically significant impairment (e.g., mild impairment = -1.5 SD; moderate impairment =-2.0 SD), a change in .5 SD equates to a categorical difference in their overall severity rating. To conduct our equivalence test, we will compute the difference in the z-score between the FF and TeleNP conditions and compute the mean difference and a 90% confidence interval based on a t-test. This results in an equivalence test with an alpha=0.05. If the entirety of bounds of the 90% confidence interval are between (-.5SD, .5SD), then the two assessments will be considered equivalent. We will repeat this computation stratified by referring diagnosis (typical vs. atypical), and also by sex or race/ethnicity (white vs. non-White).

For **Aim 2**, we will compute a 3x3 table with the rows as TeleNP diagnosis and the columns as FF diagnosis to summarize the results. To assess the equivalence of TeleNP and FF for each condition we will create 3, 2x2 tables. For example, when assessing for differences in typical AD we will collapse over atypical AD and Not AD. Following prior work³⁵, we will compute the difference proportion of typical AD for the TeleNP and FF setting and construct a 90% confidence interval. A difference of proportions greater than 5% will be considered a clinically meaningful difference. If the 90% confidence interval is between (-5%,5%), then the two modalities will be considered equivalent. We will repeat this process for the two other neuropsychologist-determined categories (atypical AD, Not AD). We will conduct the same analyses, stratified by severity. We will assess whether the neuropsychologists' diagnosis is equivalent to the Flexible Assessment by repeating the above analysis using the Flexible vs FF diagnosis (i.e., diagnosis reported prior to initiating Flexible Assessment).

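### Aim 1 sets out to determine whether TeleNP validity differs by referral diagnosis, but the SAP plans only a separate equivalence interval in each group and no typical-minus-atypical estimate

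*Combined protocol and SAP*

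**What the plan says.** Section I (Specific Aims) puts the question in two ways. Aim 1b asks "Is this equivalence consistent across referral diagnoses", and the goal statement that follows says the Aim will "determine whether the validity of TeleNP differs based on referral diagnosis". The Outcome Measure(s) section restates the goal for the domain z-scores: they should show "whether complexity of referral impacts comparability of test results".

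For Aim 1, section IV.F takes each patient's FF-versus-TeleNP difference in z-score and will "compute the mean difference and a 90% confidence interval based on a t-test". If the whole interval lies within ±0.5 SD, "then the two assessments will be considered equivalent". The referral-diagnosis question is then covered by one sentence: "We will repeat this computation stratified by referring diagnosis (typical vs. atypical), and also by sex or race/ethnicity (white vs. non-White".

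No section gives a between-group difference, a modality-by-diagnosis term, or a rule for reading the two group results together. The exploratory analysis of provider effects (Potential Scientific Problems) concerns the neuropsychologist, not the referral diagnosis.

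**The concern.** Whether validity differs by diagnosis, or whether complexity affects comparability, is a question about the gap between two groups. The planned output is one estimate, interval and verdict per group, and the only decision rule is pass or fail. The natural way to answer the stated question from that output is to compare verdicts, which can mislead in two directions:

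- One group may pass and the other fail although the modality effects are the same, through sampling error or because one group is more variable.
- Both groups may pass with effects in opposite directions. Each verdict is then correct, but neither gives the size of the between-group difference.

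The question matters here because the protocol justifies the study by asking whether TeleNP generalises to atypical presentations, and it enrols 40 patients of each kind to find out. Aim 1a is not in question.

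**Working it through.** **Inputs from the documents.** 40 typical and 40 atypical patients; 90% t-based CI; margin ±0.5 SD; four cognitive domains. The stated alpha reproduces: a 90% CI inside the margin is two one-sided tests at (1 - 0.90)/2 = 0.05.

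**Input not in the documents.** The SD of the within-person FF-minus-TeleNP difference, in z units. I assume 0.5, 0.75 and 1.0. The true modality effects used below (0, 0.10, 0.25) are also assumptions.

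**Precision**

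- Single group: half-width = t(0.95; 39) × SD/√40, with t = 1.685. This gives 0.13 / 0.20 / 0.27.
- Contrast, equal SDs: half-width = t(0.95; 78) × SD × √(1/40 + 1/40), with t = 1.665. This gives 0.19 / 0.28 / 0.37. If only 40 and 30 complete, it is 0.20 / 0.30 / 0.40.

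**Three worked cases (n = 40 per group)**

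| SD (typical, atypical) | Mean, typical | Mean, atypical | 90% CI, typical | 90% CI, atypical | Contrast (90% CI) |
|---|---|---|---|---|---|
| 0.75, 0.75 | +0.25 | +0.35 | 0.05 to 0.45, pass | 0.15 to 0.55, fail | -0.10 (-0.38 to 0.18), p = 0.55 |
| 0.75, 0.75 | +0.25 | -0.25 | 0.05 to 0.45, pass | -0.45 to -0.05, pass | 0.50 (0.22 to 0.78), p = 0.004 |
| 0.5, 1.0 | +0.25 | +0.25 | 0.12 to 0.38, pass | -0.02 to 0.52, fail | 0.00 (-0.30 to 0.30) |

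In the third row the standard error is √(0.25/40 + 1/40) = 0.177. With Welch df 57.4, t = 1.672 and the half-width is 0.296.

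**Chance of split verdicts when the true effects are identical.** If each group passes with probability p, the chance is 2p(1 - p). Entries are p, then the split rate, per domain.

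| True effect in both groups | SD 0.5 | SD 0.75 | SD 1.0 |
|---|---|---|---|
| 0 | 1.000, 0% | 0.988, 2.5% | 0.856, 25% |
| 0.10 | 0.9996, 0.1% | 0.952, 9% | 0.781, 34% |
| 0.25 | 0.928, 13% | 0.665, 45% | 0.462, 50% |

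With SD 0.6 in typical and 0.9 in atypical patients, the split rates are 7%, 14% and 48% at effects 0, 0.10 and 0.25.

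The chance that at least one of the four domains splits, at a true effect of 0.10, is 0.4% at SD 0.5, 26 to 32% at SD 0.75 and 73 to 81% at SD 1.0. The ranges run from a correlation of 0.5 between the domain differences to independence.

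**The case against.** - **The numbered question is answered.** Aim 1b asks about consistency of equivalence, and repeating the equivalence analysis in each group addresses that. This stands for the narrow reading. The goal statement in Section I and the Outcome Measure(s) section ask more.
- **The plan never says it will infer a difference from split verdicts, and the contrast can be derived.** Both are true: the groups are independent and each mean and interval will be reported. The fault is silence, and the split rates measure a misreading the plan leaves open rather than one it prescribes.
- **The SD and effects are assumed.** Correct. If domain z-scores had unit SD in both modalities, the SD of the difference would be √(2(1 - r)). SDs of 0.5, 0.75 and 1.0 then correspond to correlations of 0.875, 0.72 and 0.50. The documents do not settle which applies, and at SD 0.5 with an effect of 0.10 or less the problem is negligible.
- **An estimate without a margin is not a decision rule either.** This stands as a caution. If readers ask only whether the 90% CI excludes zero, identical effects give a false signal in 10% of domains, and in 1 - 0.9⁴ = 34% of trials for at least one of four independent domains. The contrast should therefore be read for size and precision, not as a test.
- **Welch is a preference.** Largely so at 40/40: with SDs of 0.5 and 1.0, coverage of a nominal 90% interval is 0.900 for Welch and 0.898 for pooled. With 30 completers in the more variable atypical group it is 0.900 against 0.867. Welch loses nothing, and the atypical group is defined broadly ("AD is under consideration, but other diagnoses may be included in" the neurologist's differential), so equal spread cannot be taken for granted.

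**Conclusion.** The concern holds. A stated objective of Aim 1 has no analysis that answers it directly; the stratified intervals answer only whether equivalence is shown in each group. How far a comparison of verdicts could mislead depends on the unknown SD of the paired difference and on the true modality effect. With identical true effects, the per-domain split rate runs from essentially nil (SD 0.5, effect near zero) to about half (SD 1.0, effect 0.25), assuming 40 complete cases per group. No Aim 1a result and no within-group equivalence conclusion is affected. It is a change that should be made, because it is cheap and concerns a question central to the trial's rationale, but it is not a flaw in the main equivalence test.

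**What to change.** Keep the Aim 1a analysis and the stratified intervals as written. Add to section IV.F:

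- for each cognitive domain, the typical-minus-atypical difference in mean (FF minus TeleNP) z-score, with a 90% CI from an unequal-variance (Welch) two-sample comparison;
- a statement that this is estimation with no margin, and that whether validity differs by referral diagnosis will be judged from the estimate and its interval, not from comparing the two verdicts;
- a label of exploratory for any corresponding sex or race/ethnicity contrast.

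The cost is one or two sentences and one two-sample comparison per domain, from data already being collected, with no extra visits. The limitation to disclose is imprecision: at SD 1.0 the half-width is 0.37 to 0.40, so the contrast may not settle the question, although it would still inform the planned definitive trial.

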Aim 2: Evaluate the impact of home-based TeleNP on the differential diagnosis of typical and atypical AD. 2a. Is the neuropsychologist's diagnosis comparable across TeleNP and FF conditions? 2b. Does flexibility to incorporate additional tests (Flexible Assessment) that are not readily adaptable to video administration alter diagnostic conclusions? *Given that neuropsychologists' conceptualizations of patient presentations may differ from the referring neurologist, this Aim will appraise whether TeleNP results in the same diagnoses from neuropsychologists compared to FF (gold standard) conditions.*

Aim 3: Appraise the feasibility and acceptability of TeleNP in the evaluation of AD patients. 3a. What is the user experience of TeleNP by patients, care partners, neuropsychologists, and psychometrists? 3b. Are there barriers or unique benefits of TeleNP that may influence future use and scalability in clinical care? *This Aim will utilize mixed methods, including interviews about the user experience and surveys of intervention feasibility and acceptability, to address quantitative and qualitative aspects of TeleNP that may influence the pragmatic implementation of remote assessments in a future, definitive trial.*

II. Background and Significance:

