Face-to-face (FF) Assessment (control condition): The participant will undergo an in-person evaluation with the neuropsychologist and psychometrist at the Clinical & Translational Research Center (CTRC) or in Building 400 at CU-AMC. The standard protocol will be administered, including the interview and Core Battery. After completion of the Core Battery and submission of initial ratings, the supervising neuropsychologists may elect to have additional tests administered by the psychometrist as part of a Flexible Assessment. The Flexible Assessment will include a menu of tests that have physical/tactile stimuli (e.g., Design Fluency; Trail Making Test), all of which are excluded from the Core Battery due to lack of adaptability to video-based administration. Upon receipt of the scores from the Flexible Assessment, the neuropsychologist will complete a second form indicating any alterations to their diagnosis based on new information.

TeleNP Assessment (intervention condition): The participant will undergo a video-based TeleNP assessment using a HIPAA-compliant platform (e.g., Zoom). The participant will be at home using a study-provided tablet, and the neuropsychologist and psychometrist will administer the evaluation from either the CTRC or their CU-AMC office. During the scheduled TeleNP assessment, the standard protocol will be administered (i.e., interview and Core Battery). The psychometrist will assist with tablet collection at no direct cost to the participant (i.e., will provide a paid return box; alternatively, participant may drop off tablet if convenient to them)

Data Collection for Clinical Trial Participants:

Medical records:

--Participants will be asked to allow their past, current and future medical record information, to be placed in our RedCap database. The goal is to collect health information pertinent to cognitive functioning in older adults. Because concurrent medical conditions and treatments may impact the participants' health, it is likely that all pertinent past, current and future medical record information will be considered for inclusion in the RedCap database. This will include: symptom history and diagnostic considerations from the participants' neurology notes; laboratory results; health history (i.e., major medical problems); brain imaging results.

Demographics:

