Aim 2: Equivalence of Neuropsychologist's Diagnosis: *Considering that neuropsychologists' conceptualizations of patient presentations may differ from the referring neurologist, the goal of this Aim is to appraise whether TeleNP results in the same diagnoses from neuropsychologists compared to FF (gold standard) conditions, and determine whether inclusion of flexibility to incorporate additional tests (Flexible Assessment) that are not readily adaptable to video administration alters diagnostic considerations.* Neuropsychologist-determined diagnosis (i.e., typical AD, atypical/complex AD, not AD) and severity (i.e., subjective concerns; MCI; dementia) will be assessed immediately after the standard protocol via a REDCap survey. To clarify whether the Flexible Assessment alters the neuropsychologists' conceptualizations, neuropsychologist diagnosis and severity will also be documented after the Flexible Assessment is completed.

Aim 3: Feasibility and Acceptability of TeleNP: *This Aim will utilize mixed methods, including patient, care partner, neuropsychologist, and psychometrist interviews about the user experience and surveys of intervention feasibility and acceptability (i.e., modified UTAUT), to address quantitative and qualitative aspects of TeleNP that may influence the pragmatic implementation of remote assessments in a future, definitive trial.*

Qualitative:

- Patients and Care Partners: **A subset of diverse patients (n=20) and any associated care partners** will be invited to participate in semi-structured interviews with the psychometrist within one week of completing both FF and TeleNP conditions. We will sample for diverse perspectives, including participants from both genders and typical vs. atypical AD. These interviews will focus on the participant's user experience, guided by

UTAUT domains and specific attention to home setting and potential care partner involvement.

- Psychometrist and Neuropsychologists: The psychometrist and neuropsychologists will also participate in brief, separate interviews to garner information regarding feasibility, acceptability, and strengths/weaknesses of TeleNP; these interviews will be conducted by [name] on four occasions, with each interview occurring after completion of 20 study visits.

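### Aim 2 asks whether TeleNP and FF give each patient the same diagnosis, but the plan tests only net label proportions (±5 points) and pre-specifies no measure of agreement

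*Combined protocol and SAP*

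**What the plan says.** Section I states the purpose of Aim 2: "this Aim will appraise whether TeleNP results in the same diagnoses from neuropsychologists compared to FF (gold standard) conditions". Section IV.C (Outcome Measures) repeats this almost word for word. Question 2a asks whether the diagnoses are comparable, and the overarching goal in Section I speaks of equivalence for diagnostic adjudication.

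For the analysis, Section IV.F says "we will compute a 3x3 table with the rows as TeleNP diagnosis and the columns as FF diagnosis to summarize the results". The table is then collapsed into three 2x2 tables, one each for typical AD, atypical AD and Not AD. For each, "we will compute the difference proportion of typical AD for the TeleNP and FF setting and construct a 90% confidence interval", and the decision rule is: "If the 90% confidence interval is between (-5%,5%), then the two modalities will be considered equivalent". The rule is reused twice: "We will conduct the same analyses, stratified by severity", and the Flexible Assessment is judged "by repeating the above analysis using the Flexible vs FF diagnosis". The Flexible Assessment is elective (Section IV.B): "the supervising neuropsychologists may elect to have additional tests administered by the psychometrist as part of a Flexible Assessment".

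Section IV.B also assigns a different neuropsychologist to each of a patient's two visits, randomized and counterbalanced. Section IV.E plans exploratory analyses of provider effects. Neither document section gives a power calculation, an expected prevalence or an expected level of disagreement for Aim 2.

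**The concern.** Two questions are mixed. One is whether modality shifts how often a label is given; a difference in marginal proportions answers that. The other is whether the same patient receives the same label; only agreement answers that. In a collapsed 2x2 table, let b be the patients given the label by TeleNP only and c those given it by FF only. The net difference depends on b − c, agreement depends on b + c, and the plan makes inferences only about b − c.

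The width of a paired interval nevertheless depends on b + c. Because a different neuropsychologist rates each modality, ordinary disagreement between raters adds to b + c and can push a common category outside ±5% with no modality effect at all. The rule makes no allowance for this. A result of equivalence not shown could then be read as a modality difference, and the later definitive trial would still lack the match rate and its uncertainty.

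**Working it through.** The plan gives no Aim 2 power or precision figure to reproduce. Its use of a 90% interval as an equivalence test at one-sided alpha 0.05 is correct.

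**Inputs.** From the documents: n = 80, paired data, 90% interval, margin ±5 points. Assumed, because the documents give neither: prevalence p and kappa. A value near 40% is plausible for typical and atypical AD, since 40 patients of each are enrolled by referral and Not AD is a third option. Also assumed: the interval method. Section IV.F cites reference 35 for the approach, but the reference list available here ends at 34, so several methods were checked.

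**Step 1: which results pass.** Paired Wald interval: (b − c)/n ± 1.645 × √[b + c − (b − c)²/n]/n. At n = 80:

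- 2-2: 0 ± 1.645 × √4/80 = ±4.1 points, passes.
- 2-1: −2.3 to 4.8, passes.
- 2-0: upper limit 5.4, fails.
- 3-3: ±5.04, fails.
- 4-4 (10% balanced discordance): ±5.8, fails.

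The full passing set is 0-0, 1-0, 1-1, 2-1 and 2-2, in either direction. A pass therefore needs at most 4 discordant patients, and not every such split passes. Across the paired methods checked the limit is 2 to 6.

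**Step 2: chance of passing with no net effect.** With equal marginals, discordance = 2p(1 − p)(1 − kappa). At p = 0.4 this is 0.48 × (1 − kappa), or 4.8%, 9.6% and 14.4% at kappa 0.9, 0.8 and 0.7. Summing exact trinomial probabilities over the passing sets:

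| Category, method | kappa 0.9 | kappa 0.8 | kappa 0.7 |
|---|---|---|---|
| 40%, Wald | 41% | 5.5% | 0.3% |
| 40%, Agresti-Min or Bonett-Price | 25% | 3.2% | 0.2% |
| 40%, Tango | 10% | 0.6% | 0.02% |
| 40%, Newcombe, no continuity correction (approximate) | 44% | 10% | 1% |
| 20%, Wald | 62% | 23% | 5.5% |
| 10%, Wald | 81% | 56% | 34% |

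Stated by discordance alone, the Wald pass chance is 38% at 5%, 4.5% at 10% and 0.2% at 15%.

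**Step 3: all three categories.** With assumed prevalences of 40/50/10% and 200,000 simulated tables per scenario, all three pass (Wald) in 27%, 2% and 0.05% of trials at kappa 0.9, 0.8 and 0.7. True overall agreement in those scenarios is 94%, 88% and 83%.

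**Step 4: strata.** If a severity stratum had 40 patients (assumed), one discordant patient gives an upper Wald limit of 2.5 + 1.645 × √(1 − 1/40)/40 × 100 = 6.6 points, so the rule fails.

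**Step 5: a pass with poor agreement.** Suppose each modality labels 4 of 80 patients and 2 are in common, so b = c = 2. The Wald interval is ±4.1 and passes. Observed agreement is 76/80 = 0.95; chance agreement is 0.05² + 0.95² = 0.905; kappa = 0.045/0.095 = 0.47. TeleNP confirms 2 of the 4 FF labels.

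**Step 6: an unpaired interval.** If one were used, the half-width at p = 0.4 would be 1.645 × √(2 × 0.4 × 0.6/80) = 12.7 points, and the rule could pass only up to about 3.8% prevalence.

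**The case against.** The plan's operational language is mostly equivalence, and a marginal test fits that reading. The 3x3 table is already pre-specified, and agreement can be read from it. At n = 80 a pass under a paired interval implies at most 6 discordant patients, which is at least 74/80 = 92.5% raw agreement, so large offsetting reclassifications cannot pass. The rare-category example passes under Wald but fails under Tango and, very narrowly, under Newcombe. Rater assignment is randomized and counterbalanced, so average rater tendencies should largely balance out of the net difference, whereas kappa retains rater disagreement. The 40% and kappa 0.9 are assumptions, and at lower prevalence the Wald rule passes more often than not at kappa 0.9. This is a pilot that claims no power, and the plan does not say that a crossing interval shows a difference. Adding agreement leaves the pass probabilities unchanged.

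Much of this stands. The marginal test is defensible and should stay, and the main risk is an uninformative result rather than a false pass. It does not remove the gap. The stated aim concerns the same diagnoses, and a table without a named statistic and interval leaves the choice of measure until the data have been seen. Pilot status excuses low power but not a missing estimand, and an estimate of agreement is what a pilot can usefully deliver.

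**Conclusion.** The concern holds. That no agreement statistic or interval is pre-specified is plain from the text and rests on no assumption. That a common category would probably miss ±5% rests on a prevalence near 40%, kappa no higher than about 0.9, 80 complete pairs and a paired interval; under every method tried, the chance of passing is then below one half. It does not extend to uncommon categories, where a pass is more likely but says less about agreement on the label. As an indication of scale, 80% power for the ±5% rule with zero true difference needs about 165 pairs at kappa 0.9 and 329 at kappa 0.8 (p = 0.4; discordance × [(1.645 + 1.282)/0.05]²). This should be fixed before analysis; it does not threaten the conduct of the study.

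**What to change.** In Section IV.F:

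- Keep the ±5% marginal analysis, name a paired interval method for it, and state that an interval crossing ±5% is inconclusive rather than evidence of a difference.
- Add, as a pre-specified co-reported analysis for Aim 2a, overall percent agreement and Cohen's kappa with 95% intervals from the 3x3 table, plus positive and negative agreement with FF for each category.
- State that TeleNP-FF discordance combines rater and modality differences, and that kappa depends on prevalence.
- Report the same for Flexible versus FF among patients who had the elective Flexible Assessment, giving the denominator.

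The cost is a few sentences and a few lines of code on data already planned. The downside is slightly more analysis and an agreement estimate without a threshold, since the documents give none. Precision at n = 80 is useful: 68/80 = 85% has a Wilson 95% interval of 76% to 91%, and the kappa half-width is about 0.09, 0.12 and 0.14 at kappa 0.9, 0.8 and 0.7 (40/50/10% prevalence). Positive agreement by category is less precise: 27/32 = 84% (68% to 93%) for a 40% category and 7/8 = 88% (53% to 98%) for a 10% category.
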